11.6.2 Cystic Fibrosis Questionnaire-Revised

Subjects will be asked to complete the CFQ-R in their native language, if validated translations are available.^{18, 19} The CFQ-R will be completed before any other study assessments are performed at the study visit. The questionnaires provide information about demographics; general quality of life, school, work, or daily activities; and symptom difficulties (pertaining to CF). Copies of the CFQ-R will be provided in the Study Reference Manual. Validated translations of the CFQ-R, if available, will be provided for participating centers in non-English-speaking countries.^{20, 21}

11.7 Safety

Safety evaluations will include AEs, clinical laboratory assessments, ECGs, clinical evaluation of vital signs, pulse oximetry, and physical examinations (PEs).

11.7.1 Adverse Events

All AEs will be assessed, documented, and reported in accordance with ICH GCP guidelines. Section 13.1 outlines the definitions, collection periods, criteria, and procedures for

documenting, grading, and reporting AEs. A separate document that details AE case report form (CRF) completion guidelines for investigators as well as training will be provided.

11.7.2 Clinical Laboratory Assessments

Blood and urine samples will be analyzed at a central laboratory, with the exception of the urine pregnancy tests which will be performed and analyzed at the site. Fasting is not required. The safety laboratory test panels are shown in Table 11-2.

Laboratory test results that are abnormal and considered clinically significant will be reported as AEs.

Table 11-2 Safety Laboratory Test Panels

Serum Chemistry	Hematology ^a	Urinalysis ^b
Glucose	Hemoglobin	Leukocyte esterase
Blood urea nitrogen ^c	Erythrocytes	Nitrite
Creatinine	Mean corpuscular hemoglobin	Urobilinogen
Sodium	Mean corpuscular hemoglobin concentration	Urine protein
Potassium	Mean corpuscular volume	pH
Calcium	Reticulocytes	Urine blood
Chloride	Platelets	Specific gravity
Magnesium	Leukocytes	Urine ketones
Bicarbonate	Differential (absolute and percent):	Urine bilirubin
Phosphate	Eosinophils	Urine glucose
Total bilirubin, direct bilirubin	Basophils	
Alkaline phosphatase	Neutrophils	
Aspartate transaminase	Lymphocytes	
Alanine transaminase	Monocytes	
Lactate dehydrogenase	Coagulation Studies	
Gamma-glutamyl transpeptidase	Activated partial thromboplastin time	
Protein	Prothrombin time	
Albumin	Prothrombin time International	
Lipase	Normalized Ratio	
Haptoglobin ^d		
Creatine kinase		
Cholesterol		
Triglycerides		

^a Blood smears will be saved for future evaluation, if needed.

^b If urine is positive for leukocyte esterase, nitrite, protein, or blood, microscopic examination of urine will be performed for leukocytes, erythrocytes, crystals, bacteria, and casts.

^c If blood urea nitrogen cannot be collected, urea may be substituted.

^d Haptoglobin will be analyzed only if there is evidence of possible hemolysis as determined by the site.

Pregnancy (β -human chorionic gonadotropin) Tests for Females of Childbearing Potential:

Serum samples will be analyzed for β -human chorionic gonadotropin at the central laboratory. Urine pregnancy tests will be performed at the site. The urine pregnancy test must be negative before the first dose of study drug (Day 1 Visit for Part 1 and Part 3; Day -28 Visit for Part 2). Pregnancy tests shown in [Table 3-1](#), [Table 3-2](#), and [Table 3-3](#) are required in all countries. s. Additional urine pregnancy tests may be required according to country-specific regulations and/or requirements.

Follicle-stimulating Hormone (Screening Period only): Blood sample for FSH will be measured for any suspected postmenopausal female with at least 12 months of continuous spontaneous amenorrhea. Serum FSH levels must be within the postmenopausal reference range of the performing laboratory to be considered postmenopausal.

CFTR genotype (Screening Period only): *CFTR* genotyping will be performed for all subjects. If the screening *CFTR* genotype result is not received before randomization, a previous *CFTR* genotype laboratory report may be used to establish eligibility. Subjects who have been randomized and whose screening genotype does not confirm study eligibility must be discontinued from the study (Section 9.10).

G6PD Activity Test (Screening Period only): Blood samples will be collected for the G6PD activity test, which will be performed in an established laboratory that runs the assay routinely. The use of a local laboratory that routinely runs quantitative G6PD activity assays is acceptable as an alternative to the central laboratory.

Additional Evaluations: Additional clinical laboratory evaluations will be performed at other times if judged to be clinically appropriate.

For purposes of study conduct, the central laboratory must be used for all laboratory tests with the exception of the G6PD activity test. Local laboratories may be used at the discretion of the local investigator for management of urgent medical issues. If a local laboratory test value is found to be abnormal and clinically significant, it will be verified by the central laboratory as soon as possible after the investigator becomes aware of the abnormal result. If it is not possible to send a timely specimen to the central laboratory (e.g., the subject was hospitalized elsewhere), the investigator may base the assessment of an AE on the local laboratory value.

11.7.3 Physical Examinations and Vital Signs

A PE of all body systems will be done at screening and select study visits. At other visits, symptom-directed PEs can be done at the discretion of the investigator or healthcare provider.

A complete PE includes a review of the following systems: head/neck/thyroid; eyes/ears/nose/throat (EENT); respiratory; cardiovascular; lymph nodes; abdomen; skin; musculoskeletal; and neurological. Breast, anorectal, and genital examinations will be performed when medically indicated. After screening, any clinically significant abnormal findings in PEs will be reported as AEs.

The abbreviated PE will include an assessment of the following body systems: EENT, cardiovascular system, respiratory system, abdomen, and skin.

Vital signs include blood pressure (systolic and diastolic), temperature (oral), pulse rate, and respiration rate. These will be assessed following at least a 5-minute rest in the seated position. Vital signs will be assessed according to [Table 3-1](#), [Table 3-2](#), and [Table 3-3](#).

11.7.4 Pulse Oximetry

Arterial oxygen saturation by pulse oximetry will be measured after at least a 5-minute rest (seated) and before study drug dosing. At visits when study drug is taken at the site, pulse oximetry will be collected before the morning dose. This is a noninvasive measure of oxygen delivery to the tissues and has been correlated with clinical status and lung function.

11.7.5 Electrocardiograms

Standard 12-lead ECGs will be performed using a machine with printout according to the [Table 3-1](#), [Table 3-2](#), and [Table 3-3](#). Additional standard 12-lead ECGs will be performed at any other time if clinically indicated.

A subject should be rested for at least 5 minutes before an ECG is performed.

The ECG traces will be manually read at the study site at the Screening Visit and Safety Follow-up Visit. A printout of the ECG traces will be made for safety review by the investigator and maintained with source documentation. Clinically significant ECG abnormalities occurring during the study through the Safety Follow-up Visit will be recorded as AEs.

Study sites should use QTcF unless they receive approval from the medical monitor to use QTcB.

To ensure safety of the subjects, a qualified individual at the study site will make comparisons to baseline measurements. If the QTcF is increased by >60 msec from the baseline or an absolute QTcF value is ≥ 500 msec for any scheduled ECG, 2 additional ECGs will be performed approximately 2 to 4 minutes apart to confirm the original measurement. If either of the QTcF values from these repeated ECGs remains above the threshold value (>60 msec from baseline or ≥ 500 msec), a single ECG will be repeated at least hourly until QTcF values from 2 successive ECGs fall below the threshold value that triggered the repeat measurement. A subject with a QTcF value above the threshold will discontinue dosing. Further details pertaining to ECGs will be provided to sites in a separate document (ECG Manual).

11.7.6 Pregnancy and Contraception

The effects of VX-659 monotherapy or in TC with TEZ and IVA or VX-561 on conception, pregnancy, and lactation in humans are not known. VX-659, TEZ, IVA, and VX-561 did not show genotoxic potential in a standard battery of in vitro (Ames test or micronucleus in cultured mammalian cells) and in vivo (rodent micronucleus) studies. VX-659, TEZ, and IVA also did not show genotoxic potential in chromosomal aberration studies. Reproductive toxicology studies of VX-659, TEZ, and IVA have not shown teratogenicity in rats and rabbits.

11.7.6.1 Contraception

Contraception requirement for the couple is waived for the following:

- True abstinence for the subject, when this is in line with the preferred and usual lifestyle of the subject. Periodic abstinence (e.g., calendar, ovulation, symptothermal, postovulation methods) and withdrawal are not acceptable methods of contraception. True abstinence must be practiced from the Screening Visit through 90 days after the last dose of study drug.
- If the male is infertile (e.g., bilateral orchiectomy). If a male subject is assumed to have complete bilateral absence of the vas deferens, infertility must be documented before the first

dose of study drug (e.g., examination of a semen specimen or by demonstration of the absence of the vas deferens by ultrasound).

- If the female is of non-childbearing potential. To be considered of non-childbearing potential, the female must meet at least 1 of the following criteria:
 - Postmenopausal: Amenorrheic for at least 12 consecutive months and a serum FSH level within the laboratory’s reference range for postmenopausal females.
 - Documented hysterectomy or bilateral oophorectomy/salpingo-oophorectomy.

Note: All other females (including females with tubal ligations and females who do not have a documented bilateral oophorectomy) will be considered to be of childbearing potential.

- Same sex relationships

For subjects for whom the contraception requirement is not waived, study participation requires a commitment from the subject that at least 1 acceptable method of contraception is used as a couple. Methods of contraception must be in successful use from signing of consent, approximately 28 days before the first dose of study drug (unless otherwise noted), and until 90 days following the last dose of study drug. Additional contraception requirements may need to be followed according to local regulations and/or requirements. Acceptable methods of contraception are listed in Table 11-3.

Table 11-3 Acceptable Methods of Contraception

	Male Subjects and Their Female (Non-study) Partners	Female Subjects and Their Male (Non-study) Partners
Vasectomy 6 months or more previously, with a documented negative postvasectomy semen analysis for sperm	Yes	Yes
Bilateral tubal occlusion (e.g., ligation) performed at least 6 months previously.	Yes	Yes
Male or female condom with or without spermicide ^a	Yes	Yes
Female barrier contraception (such as diaphragm, cervical cap, or sponge) with spermicide	Yes	Yes
Continuous use of an intrauterine device for at least 90 days before the first dose of study drug.		
Hormone-releasing	Yes	No ^b
Non-hormone releasing	Yes	Yes
Hormonal contraceptives, if successfully used for at least 60 days before the first dose of study drug.	Yes	No ^b

^a A female condom cannot be used with a male condom due to risk of tearing.

^b Hormone-releasing intrauterine devices and hormonal contraceptives are not considered an acceptable method in female study subjects; however, female subjects are not required to discontinue their use of hormone-releasing intrauterine devices or hormonal contraceptives.

Additional notes:

- Male subjects must not donate sperm during the period starting from the first dose of study drug until 90 days after the last dose of study drug.

- Female subjects should not nurse a child during the period starting from the first dose of study drug until 90 days after the last dose of study drug.
- For male subjects with a female partner of childbearing potential, the couple must not plan to become pregnant during the study or within 90 days after the last study drug dose.

11.7.6.2 Pregnancy

Subjects will be counseled to inform the investigator of any pregnancy that occurs during study treatment and for 90 days after the last dose of study drug.

If a female subject or the female partner of a male subject becomes pregnant while participating in the study, other than a female partner as the result of artificial insemination using sperm banked by the male subject before the first dose of study drug, study drug will be permanently discontinued immediately. The investigator will notify the medical monitor and Vertex GPS within 24 hours of the site's knowledge of the subject's (or partner's) pregnancy using the Pregnancy Information Collection Form.

If confirmed to be on active drug, the subject or partner will be followed until the end of the pregnancy and the infant will be followed for 1 year after the birth, provided informed consent is obtained. A separate ICF will be provided to explain these follow-up activities. Pregnancy itself does not constitute an AE.

12 STATISTICAL AND ANALYTICAL PLANS

This section presents a summary of the planned safety analyses and clinical pharmacology analyses for this study. Safety statistical analysis details will be provided in the statistical analysis plan (SAP) for this study, and clinical pharmacologic analysis details will be provided in the clinical pharmacology analysis plan (CPAP), both of which will be finalized before clinical database lock.

Final analyses will take place after all subjects have completed the study, all data have been entered in the clinical study database, and the database has been locked.

12.1 Sample Size and Power

12.1.1 Primary Objectives

The primary objectives of the study are the evaluation of safety and tolerability, and efficacy of VX-659 in TC with TEZ and either IVA or VX-561. The sample size calculations described below are deemed adequate to evaluate the objectives of the study, based on clinical and statistical considerations.

12.1.1.1 Safety and Tolerability

The primary safety endpoint is the incidence of AEs. Approximately 105 subjects will be randomized in the study with approximately 81 subjects receiving VX-659 in TC. The sample size for each treatment group will provide sufficient data for a descriptive analysis of AEs.

12.1.1.2 Efficacy

The primary efficacy endpoint is the absolute change from baseline in ppFEV₁ through the Day 29 Visit in all parts. A sample size of 18 subjects per treatment group provides at least 90% power to detect a mean within-group change of 7 percentage points.

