Assessments **Safety:** AEs, clinical laboratory assessments, ECGs, vital signs, pulse oximetry, physical examinations (PEs)
Efficacy: spirometry, CFQ-R
PD: sweat chloride
PK: VX-659, TEZ, M1-TEZ, IVA, M1-IVA, VX-561
[REDACTED]

Statistical Analyses **Primary Objectives**

The safety analysis will be descriptive only.

The primary efficacy endpoint is the absolute change from baseline through the Day 29 Visit for ppFEV₁

All ppFEV₁ hypothesis tests will be performed within the mixed-effects model for repeated measures (MMRM) framework at a 5% alpha level, with appropriate adjustment for baseline covariates. The null within-group hypothesis of no difference in the mean absolute change from baseline through the Day 29 Visit for ppFEV₁ in all treatment groups, by part, will be tested using MMRM. The adjusted means and 2-sided 95% confidence intervals of the average treatment effects through the Day 29 Visit for all within-group and between-group comparisons will be estimated within MMRM.

Secondary Objectives

The PD endpoint is the absolute change in sweat chloride from baseline through the Day 29 Visit. In Part 1, the null hypothesis of the lack of a decreasing dose-response trend in the mean absolute change from baseline through the Day 29 Visit for sweat chloride between the TC dose groups and placebo will be tested using a multiple comparisons procedure based on the 1-sided maximum *t*-statistic. The adjusted means and 2-sided 95% confidence intervals of the average treatment effects through the Day 29 Visit, for all within-group and between-group comparisons, will be estimated within MMRM.

Interim Analyses

Interim analyses (IAs) may be conducted for any part of the study after at least 50% of subjects in the part have completed the Day 15 Visit. Each IA will only include data for a single part of the study.

IDMC Reviews

An independent monitoring committee (IDMC) will conduct safety reviews of study data as outlined in the IDMC charter.

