9 STUDY IMPLEMENTATION

9.1 Study Design

This is a Phase 2, randomized, double-blind, placebo- and TEZ/IVA-controlled, parallel-group, 3-part, multicenter study. All parts will be conducted concurrently. Subjects may not participate in more than 1 part.

Key study elements of each part are summarized in Table 9-1, treatment arms and planned doses are shown in Table 9-2, and a schematic of the study design is shown in Figure 9-1. Study visits and assessments are shown in Table 3-1 (Part 1), Table 3-2 (Part 2), and Table 3-3 (Part 3).

Table 9-1 Key Study Elements by Part

Element	Part 1	Part 2	Part 3 (optional)
Study population			
Genotype(s)	F/MF	F/F	F/MF
Age	≥18 years	≥18 years	≥18 years
ppFEV ₁ criteria	≥40 to ≤90	≥40 to ≤90	≥40 to ≤90
Number of subjects	Approximately 54	Approximately 27	Approximately 24
Randomization			
Ratio	1:1:2:2 (placebo:TC-low:TC-mid:TC-high)	1:2 (TEZ/IVA:TC-high)	1:3 (placebo:TC2-high)
Stratification	ppFEV ₁ (<70, ≥70)	ppFEV ₁ (<70, ≥70)	ppFEV ₁ (<70, ≥70)
Study design	Parallel group	Parallel group	Parallel group
Control	Placebo	TEZ/IVA	Placebo

F/F: homozygous for *F508del*; F/MF: heterozygous for *F508del* and a minimal *CFTR* function mutation that is not expected to respond to TEZ, IVA, or TEZ/IVA; IVA: ivacaftor; ppFEV₁: percent predicted forced expiratory volume in 1 second; TC: triple combination; TEZ: tezacaftor

Table 9-2 Treatment Arms and Planned Doses by Part

	Period 1			Period 2	
	VX-659 Dosage	TEZ Dosage	IVA Dosage	TEZ Dosage	IVA Dosage
Part 1					
TC-high	400 mg qd	100 mg qd	150 mg q12h	100 mg qd	150 mg q12h
TC-mid	240 mg qd	100 mg qd	150 mg q12h	100 mg qd	150 mg q12h
TC-low	80 mg qd	100 mg qd	150 mg q12h	100 mg qd	150 mg q12h
Triple placebo	Placebo	Placebo	Placebo	Placebo	Placebo
Part 2^a					
TEZ/IVA	Placebo	100 mg qd	150 mg q12h	100 mg qd	150 mg q12h
TC-high	400 mg qd	100 mg qd	150 mg q12h	100 mg qd	150 mg q12h

Part 3 (optional)

[figure not shown]
	VX-659 Dosage	Period 1 TEZ Dosage	VX-561 Dosage
TC2-high	400 mg qd	100 mg qd	200 mg qd
Triple placebo	Placebo	Placebo	Placebo

IVA: ivacaftor; q12h: every 12 hours; qd: daily; TC: triple combination; TEZ: tezacaftor

[figure not shown]
^a In Part 2, all subjects will also receive TEZ 100 mg qd/IVA 150 mg q12h during the Run-in Period

Figure 9-1 Schematic of Study Design

[figure not shown]
Part 1: Subjects With F/MF Genotypes

Part 2: Subjects With F/F Genotype

Part 3: Subjects with F/MF Genotypes (optional)

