8.3.1.1 Primary Analysis of the Primary Efficacy Variable

8.3.1.1.1 All Parts: Period 1 in the Treatment Period

The null hypothesis to be tested is that the mean absolute within-group change from baseline in ppFEV₁ through Day 29 is zero for VX-659 in TC with TEZ and either IVA or VX-561, for each part, separately. A 2-sided *p*-value of 0.05 or less will be interpreted as sufficient evidence to reject the null hypothesis.

The primary analysis will be performed using a mixed-effects model for repeated measures (MMRM) with change from baseline in ppFEV₁ as the dependent variable for each part, separately. For Part 1, the analysis will include 4 treatment groups: placebo, TC-low, TC-mid, and TC-high. For Part 2, the analysis will include 2 treatment groups: placebo + TEZ/IVA, and TC-high (VX-659 + TEZ/IVA). For Part 3, the analysis will include 2 treatment groups: placebo and TC2-high (VX-659+TEZ+VX-561). The model will include treatment group, visit, and treatment-by-visit interaction as fixed effects and subject as a random effect, with the continuous baseline ppFEV₁ as a covariate, and will include all data from each treatment group and visit during Period 1 in the analysis. The model will be estimated using restricted maximum likelihood. Denominator degrees of freedom for the F test for fixed effects will be estimated using the Kenward-Roger approximation. An unstructured covariance structure will be used to model the within-subject errors. If the model estimation does not converge, a reduced compound symmetry covariance structure will be used instead. Conditional on the observed data and covariates, missing ppFEV₁ data due to treatment or study discontinuation will be assumed to be missing at random; consequently, no imputation of missing data will be performed.

[figure not shown]
The adjusted means and 95% confidence intervals (CI) of the average treatment effect through Day 29 for each TC, with a 2-sided *p*-value will be estimated within MMRM using PROC MIXED in SAS, for all within-treatment and between-treatment comparisons, for each part, separately. Contrasts based on the fixed effects in the model, defined at the baseline covariate mean for the combined treatment groups using unique subjects in the FAS who have at least one post-baseline measurement through Day 29, will be used to estimate the average treatment effect across post-baseline visits through Day 29.

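### The primary-endpoint power statement assumes 18 subjects per group, but TC-low, also tested within-group in the primary analysis, has 9 and no stated power

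*Protocol*

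**What the plan says.** Protocol 12.1.1.2 names the absolute change in ppFEV1 through Day 29 as the primary efficacy endpoint for every part and then makes one power statement: "A sample size of 18 subjects per treatment group provides at least 90% power to detect a mean within-group change of 7 percentage points". SAP 6.2.1.2 repeats it. Neither gives the SD of the change or the test behind the figure, and neither shows a redaction there.

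The Part 1 allocation in protocol Table 9-1 is "1:1:2:2 (placebo:TC-low:TC-mid:TC-high"), applied to about 54 subjects. The synopsis schematic prints N=9 for TC-low.

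SAP 8.3.1.1.1 sets the primary null hypothesis as a mean within-group change that "through Day 29 is zero for VX-659 in TC with TEZ and either IVA or VX-561, for each part, separately". It lists TC-low among the four groups of the Part 1 model and gives the decision rule: "A 2-sided *p*-value of 0.05 or less will be interpreted as sufficient evidence to reject the null hypothesis". The protocol synopsis goes further and applies the within-group test to every treatment group, in an MMRM "framework at a 5% alpha level, with appropriate adjustment for baseline covariates".

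The other power statement, for 54 subjects in protocol 12.1.2, concerns the sweat chloride dose-response trend. No ppFEV1 power is given for a group of 9.

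**The concern.** The power sentence presents 18 as the size of a treatment group. Four arms have that size: TC-mid and TC-high in Part 1, TC-high in Part 2 and TC2-high in Part 3. The fifth triple-combination arm, TC-low, has half as many subjects and faces the same primary test at the same significance level.

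What is at stake is how a TC-low result would be read. Protocol 9.3.2 expects clinical benefit at all three Part 1 doses, and TC-low will have its own p-value. If that p-value exceeds 0.05 next to an unqualified 90% power statement, a reader may conclude that the 80 mg arm had no effect, when the smaller allocation could explain the result. Without the SD, the reader can neither check the 90% nor carry it to n=9.

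**Working it through.** **Arm sizes.** Part 1: 54/6 = 9 per unit of the 1:1:2:2 ratio, so placebo 9, TC-low 9, TC-mid 18, TC-high 18. Part 2: 27 × 2/3 = 18 on TC-high. Part 3: 24 × 3/4 = 18 on TC2-high. Cross-check: 9 + 18 + 18 + 18 + 18 = 81, the number on VX-659 given in protocol 12.1.1.1.

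**Inputs.** Change to detect 7 points, power at least 90% at n=18 (protocol 12.1.1.2); alpha 0.05 (synopsis), two-sided (SAP 8.3.1.1.1). The SD is not stated. No dropout allowance is stated and none is applied.

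**Formula.** Power = P(T > t_crit), where T is noncentral t with noncentrality 7√n/SD and t_crit is the 97.5% point of t on the same degrees of freedom.

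**The plan's own figure.** It cannot be reproduced without an SD. It can be inverted: the largest SD compatible with 90% at n=18 is the one that gives exactly 90%.

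*One-sample t (df = n − 1)*
- n=18, df 17, t_crit 2.110: SD = 8.63 gives noncentrality 7 × 4.243/8.63 = 3.44 and power 90.0%.
- n=9, df 8, t_crit 2.306, same SD: noncentrality 7 × 3/8.63 = 2.43 and power 57.1%.

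*Pooled degrees of freedom* (approximating the Part 1 MMRM: 54 subjects − 4 groups − 1 covariate = 49, t_crit 2.010)
- n=18: SD = 8.98 gives noncentrality 29.70/8.98 = 3.31 and power 90.0%.
- n=9, same SD: noncentrality 21/8.98 = 2.34 and power 63.0%.

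**Smaller SDs.** The plan says at least 90%, so the sponsor's SD may be lower:

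| Assumed SD | n=18, one-sample t | n=9, one-sample t | n=9, pooled df 49 |
|---|---|---|---|
| 8.63 | 90.0% | 57.1% | 66.5% |
| 8 | 93.8% | 63.5% | 73.0% |
| 7 | 97.9% | 74.8% | 83.7% |
| 6 | 99.6% | 86.4% | 92.9% |

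**SD at which TC-low reaches 90% for 7 points.** About 5.66 (one-sample t) or 6.35 (pooled). At SD 5.66 an arm of 18 would have about 99.9% power by the one-sample t.

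**Change detectable with 90% power at n=9,** if power at n=18 is exactly 90%: 10.7 points (one-sample t), or 7 × √2 = 9.9 points (pooled, where the degrees of freedom do not change with n).

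**The case against.** The sentence can be read as conditional: a group of 18 has at least 90% power. Nothing in the documents contradicts that, and the plan nowhere says that TC-low has 18 subjects or 90% power. The arm sizes are disclosed, and the total of 81 on VX-659 agrees with 9 in TC-low. This stands to the extent that the sentence is incomplete and not a miscalculation. It does not make the sentence adequate. It is the only power statement for an endpoint analysed in all parts, it gives 18 as the per-group size, and a primary triple-combination test falls outside it.

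A reader might also infer that TC-low power is simply 57%. The documents do not support that. The figure comes from treating a floor of 90% as exactly 90%, which gives the largest SD the statement allows, and from a one-sample test where the plan uses a model fitted to all four Part 1 groups. It is the low end of a range.

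A reader might extend the point to between-group comparisons or to the control arms. The plan claims no between-group power for ppFEV1, and its primary null is within-group. Nor is there reason to expect a 7-point within-group gain on placebo or on continued TEZ/IVA.

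Finally, confidence intervals are planned for every group, there is no multiplicity adjustment, and no decision rule depends on TC-low reaching significance. These points limit the consequence. They do not supply the missing power.

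**Conclusion.** The concern holds as a gap between the power statement and the design. The stated size of 18 and power of at least 90% do not apply to TC-low, which has 9 subjects and is tested within-group in the primary analysis. This much follows from the text and needs no assumed SD.

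The size of the shortfall is conditional. If power at n=18 is exactly 90% at two-sided 5%, TC-low power is about 57% to 63%, depending on whether the one-sample or the pooled degrees of freedom are used. At SD 7 it is about 75% to 84%. TC-low would match the stated 90% only at an SD of about 5.7 or less (one-sample t) or 6.4 or less (pooled). At those values the arms of 18 would have more than 99% power, and a description of at least 90% would be unusually modest. Unequal allocation is a legitimate choice and is not in question.

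**What to change.** In protocol 12.1.1.2 and SAP 6.2.1.2:

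- limit the statement of at least 90% power to the arms of 18: TC-mid and TC-high in Part 1, TC-high in Part 2, TC2-high in Part 3;
- give the SD of the ppFEV1 change and the test used in the calculation;
- state the power for TC-low at n=9, calculated from that same SD and test.

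The TC-low figure should come from the sponsor's own SD. The 57% to 63% above rests on a back-solved value and should not be copied into the plan.

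This is a wording change. Enrolment, allocation and analysis stay as they are, and the only cost is a less favourable stated figure for TC-low.
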